HBs antigen test	
Test was implemented: In a case where “Hbs antigen test” in the survey sheet was implemented
 
Test was not implemented: In a case where “Hbs antigen test” in the survey sheet was not implemented
 
Unknown/not described: Other than above situations

HBs antibody test	
Test was implemented: In a case where “Hbs antibody test” in the survey sheet was implemented
 
Test was not implemented: In a case where “Hbs antibody test” in the survey sheet was not implemented
 
Unknown/not described: Other than above situations

HBC antibody test	
Test was implemented: In a case where “Hbc antibody test” in the survey sheet was implemented
 
Test was not implemented: In a case where “Hbc antibody test” in the survey sheet was not implemented

Name of data	Derivation and calculation method
	Unknown/not described: Other than above situations
HBV-DNA quantitative test	Test was implemented: In a case where “HBV-DNA quantitative test” in the survey sheet was implemented Test was not implemented: In a case where “HBV-DNA quantitative test” in the survey sheet was not implemented Unknown/not described: Other than above situations
Chest X-ray test	When the start date of the initial administration of this drug is defined as 1 and previous day of the start date of the initial administration is defined as -1, patients in which date of chest X-ray is included between -90 and -1, are deemed to undergo chest X-ray. In addition, data included in the survey sheet should be used.
CT scanning	When the start date of the initial administration of this drug is defined as 1 and previous day of the start date of the initial administration is defined as -1, patients in which date of CT scanning is included between -90 and -1, are deemed to undergo CT scanning. In addition, data included in the survey sheet should be used.
Other image tests	When the start date of the initial administration of this drug is defined as 1 and previous day of the start date of the initial administration is defined as -1, patients in which date of other image tests is included between -90 and -1, are deemed to undergo other image tests. In addition, data included in the survey sheet should be used.

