Chest X-ray and CT scanning	Either of “Chest X-ray” or “CT scanning” is implemented (if there is no check mark in box for implementation although test results are described, tests are deemed to have been implemented”). Tests were not implemented: Other than above situations
Drug previously used	Of data in which there are any descriptions about “previously used drug/previous treatment for gastro-intestinal Behcet disease”, data excluding that about previous treatment method is deemed to be previously used drug. Patients with description about previously used drug is deemed to have drug previously used. If there is no description in “previously used drug/previous treatment method for gastro-intestinal Behcet disease” and whether patients have drug previously used cannot be assessed, where there is drug previously used is deemed to be unknown/not described, and in any other situations, patients are deemed to have no drug previously used.
Presence or absence of use of previously used drug (aminosalicylic acid preparation)”	Based on “161206 drug list_addtion (Fix)CRO”, if there is a data on previously used drug corresponding to relevant drug code or there is a check mark in a box for aminosalicylic acid preparation in the survey sheet, patients are deemed to have previously received aminosalicylic acid preparation and in any other situations, patients are deemed not to have received aminosalicylic acid preparation.

Name of data	Derivation and calculation method
Presence or absence of previously used drug (steroid)	Based on “161206 drug list_addtion (Fix)CRO”, if there is a data on previously used drug corresponding to relevant drug code or there is a check mark in a box for steroid in the survey sheet, patients are deemed to have previously received steroid and in any other situations, patients are deemed not to have received steroid.
Presence or absence of previously used drug (immunomodulative drug)	Based on “161206 drug list_addtion (Fix)CRO”, if there is a data on previously used drug corresponding to relevant drug code or there is a check mark in a box for immunomodulative drug in the survey sheet, patients are deemed to have previously received immunomodulative drug and in any other situations, patients are deemed not to have received immunomodulative drug.

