Test for tuberculosis	Test was implemented: If “test for tuberculosis or IGRA test” were implemented and “chest X-ray or CT scanning” was implemented. Tests were not implemented: Other than above situations
Test of hepatitis B	Test was implemented: If “HBV-DNA quantitative test” was implemented or patients are negative for “Hbs antigen test”, “Hbs antibody test”, and “Hbc antibody test”. Tests were not implemented: Other than above situations
Responding patients	Patients who were assessed to have obtained “improvement” and “significant improvement” as level of overall improvement are defined as responding patients.

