12.5. Time of evaluation of gastrointestinal symptoms

Time Allowance at evaluation when the start date of the initial administration of this drug is defined as 1 is as follows:

Time of evaluation	Time Allowance(Day)
Administration start	until 1 (record date is day 1)
4 weeks after the administration start	15-42 (record date is day 29)
8 weeks after the administration start	43-70 (record date is day 57)
12 weeks after the administration start	71-98 (record date if day 85)
24 weeks after the administration start	155-183 (record date if day 169)

Time of evaluation	Time Allowance(Day)
52 weeks after the administration start	351-379 (record date is day 365)
76 weeks after the administration start	505-561 (record date is day 533)
104 weeks after the administration start	701-757 (record date is day 729)
128 weeks after the administration start	869-925 (record date is day 897)
156 weeks after the administration start	1065-1121 (record date is day 1093)

The latest data of that obtained within Time allowance should be included in analysis and if there is multiple data for the same day, data with the worse value (in the order of 4,3,2,1,0) should be included in analysis.

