Analysis items: Patient number, sex, age, body weight, disease duration, adverse event (presence or absence of adverse events, adverse event that occurred outside the period subject to analysis, SOC code, system organ class, PT code, disease name [PT of MedDRA], adverse event terms described by physician, onset date, days from start of administration of this drug to onset, seriousness, causal relationship, outcome, outcome

date, days to outcome date), level of overall improvement, administration status of this drug (start date of administration, last date of administration, days of administration, initial dose, maximum dose), presence or absence of complications, presence or absence of medical history, hepatitis B viral test (HBs antigen, HBs antibody, HBc antibody, HBV-DNA quantitative), tests for tuberculosis (tuberculin test, QuantiFERON test, T-spot test, chest X-ray, CT scanning, other image tests), retrieving flag (patients included in safety analysis, patients included in efficacy analysis, patients who continue to participate in clinical study, patients in whom adverse events occurred outside the period subject to safety analysis, patients who died, children, the elderly, pregnant women, patients who are lactating, patients with liver disorder, patients with renal impairment, patients with hepatitis B viral infection, patients in whom infection occurred, patients in whom malignant tumour occurred, patients in whom administration site reaction occurred, patients in whom autoimmune disease occurred, patients in whom pancytopenia occurred, patients in whom demyelinating disorder occurred, patients in whom cardiac failure congestive occurred, patients in whom interstitial pneumonia occurred, patients in whom deviation from administration rule of this drug occurred, patients in whom dose increase was made, patients with complete type Behcet disease, patients with incomplete type Behcet disease, patients with suspected Behcet disease, patients with recurrent aphthous ulcer, patients with cutaneous symptoms, patients with eye symptoms, patients with ulcer of vulva, patients with arthritis without deformity or rigidity, patients with epididymitis, patients with vascular disease, patients with moderate or higher degree central nervous lesion, patients with self-administration error, patients with detected AAA, patients who have contraindicated drug)

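### SAP 10.1 judges chest imaging by date in one entry and by a described result in another, and the tuberculosis test built on it counts missing information as not implemented

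*SAP*

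**What the plan says.** All the definitions are in SAP section 10.1.

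- **Day numbering.** The imaging entries open with "When the start date of the initial administration of this drug is defined as 1" and number the previous day -1, so there is no day 0.
- **Chest X-ray test.** "patients in which date of chest X-ray is included between -90 and -1, are deemed to undergo chest X-ray". The rule uses no check box and does not mention a result.
- **CT scanning.** The same rule: "patients in which date of CT scanning is included between -90 and -1, are deemed to undergo CT scanning".
- **Combined imaging item** (headed as X-ray *and* CT, but satisfied by either). It counts as implemented when either test is implemented, with the addition "if there is no check mark in box for implementation although test results are described, tests are deemed to have been implemented". No date is mentioned. The remainder is "Tests were not implemented: Other than above situations".
- **Test for tuberculosis.** This needs the skin or blood test and also that "chest X-ray or CT scanning” was implemented". Its remainder is again *not implemented*.
- **Tuberculin test or IGRA test.** This entry has three classes: implemented, not implemented, and unknown/not described. It carries the same parenthesis about a missing check mark.

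Two outputs use these items. List 1.4 shows "tests for tuberculosis (tuberculin test, QuantiFERON test, T-spot test, chest X-ray, CT scanning, other image tests" as separate fields. Table 1.12.1 tabulates the composite. Section 11 has a row for tuberculin/IGRA but none for the imaging item or the composite, so it does not settle their classes.

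**The concern.** One fact, whether the patient had chest imaging before treatment, is decided from different data in adjacent entries. The component entries look only at the date. The combined entry brings in a described result and a check box and does not look at the date. The SAP does not say which governs when they disagree, so two programmers following it faithfully could report different tuberculosis-screening rates in Table 1.12.1. The same patient could also appear without qualifying imaging in list 1.4 and as screened in the table.

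The second problem is the residual class. Where the survey sheet is blank on imaging, the patient becomes *not implemented*. In Test for tuberculosis, a tuberculin/IGRA status of unknown/not described goes the same way. A reader of Table 1.12.1 cannot separate patients who were not tested from patients for whom nothing was recorded.

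**Working it through.** The SAP states no figure to reproduce. The check is a comparison of the rules, case by case.

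**Inputs** (all from section 10.1): first-dose date = day 1, previous day = day -1; window for X-ray and CT = days -90 to -1; combined item = either test implemented, or a result described with the box unchecked; everything else = not implemented.

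**Three readings**

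- A: the component date rule alone.
- B: the combined entry read on the check box or described result alone.
- C: the combined entry layered on the component rule, so that imaging counts if dated in the window, or if a result is described with the box unchecked.

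Each was applied to imaging on day -91, -90, -1, 1 or 2, or with no date, crossed with box checked or not and result described or not: 6 x 2 x 2 = 24 cells. Days -91, 1, 2 and no date behave alike, as do days -90 and -1.

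| Imaging date | Box | Result described | A | B | C |
|---|---|---|---|---|---|
| Outside window, or none | checked | yes | not impl. | impl. | not impl. |
| Outside window, or none | checked | no | not impl. | impl. | not impl. |
| Outside window, or none | unchecked | yes | not impl. | impl. | **impl.** |
| Outside window, or none | unchecked | no | not impl. | not impl. | not impl. |
| Days -90 to -1 | checked | yes | impl. | impl. | impl. |
| Days -90 to -1 | checked | no | impl. | impl. | impl. |
| Days -90 to -1 | unchecked | yes | impl. | impl. | impl. |
| Days -90 to -1 | unchecked | no | impl. | not impl. | impl. |

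**What follows**

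1. Layering the entries (C) does not remove the conflict. The third row still differs from the date rule: 4 of the 24 cells, one for each of the four date situations. These are cells of a logic table, not patient frequencies.
2. Under C, rows 1 and 3 differ only in the check mark, yet the checked box gives *not implemented* and the blank box gives *implemented*. The more completely filled sheet leaves the patient unscreened.
3. Imaging dated in the window with a described result is *implemented* under all three readings. The conflict is confined to undated or out-of-window imaging, except that B also loses in-window imaging with neither a check mark nor a result.

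**Residual class.** Let N be all patients in the table, n1 those implemented, n0 those recorded as not tested or not tested in the window, and u those with no usable information, so N = n1 + n0 + u. Section 9.2 keeps unknown and not-described patients in the denominator.

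- Implemented share: n1/N with or without an unknown class.
- Not-implemented share: (n0 + u)/N as written, n0/N with an unknown class. It is overstated by u/N.

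**The case against.** The best defence is that the combined entry names the two tests as items already defined just above it, so the -90 to -1 window carries over. Its parenthesis then repairs only a missing check mark, as the identical parenthesis does for tuberculin/IGRA. That is a fair reading and it narrows the conflict: imaging with the box checked follows the date rule. It does not close it. The parenthesis still counts a described result with no date, and it assumes a status read from a check box, which the imaging entries do not use.

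The use of the variable is also limited, and this stands. Test for tuberculosis is a row in a table of patient characteristics. It is not among the factors in Tables 2.9 and 3.4, enters no significance test and defines no population. The two-class form is not unique to it either: Test of hepatitis B has the same residual rule.

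Four stronger inferences are tempting, and the document does not support them.

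- *Leaving out day 1 is an error, because the symptom baseline in section 12.5 runs* "until 1 (record date is day 1". The imaging entries define both day 1 and day -1 and then stop at -1. That looks deliberate for a check made before the first dose, and symptom and CRP baselines serve a different purpose.
- *Tuberculin or IGRA tests done after treatment began are counted.* That entry has no window, but the survey sheet is not available and may collect only pre-treatment tests.
- *The primary tuberculosis results are affected.* Tuberculosis as a primary survey item is an adverse event identified from a MedDRA list; the screening variable plays no part in it.
- *The missing unknown class lowers the screening rate.* Under section 9.2 it does not; it inflates only the not-implemented share.

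**Conclusion.** The inconsistency is real and narrow. Undated or out-of-window chest imaging with a described result and an unchecked box is not done under the X-ray and CT entries and implemented under the combined entry. Test for tuberculosis carries this into Table 1.12.1. Separately, the combined entry and Test for tuberculosis record missing information as *not implemented*, although the tuberculin/IGRA entry keeps it apart.

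The consequence is a descriptive screening rate that cannot be reproduced from the SAP alone, together with an overstated share of patients shown as untested. The size of either effect cannot be worked out. It depends on how many sheets have undated or out-of-window imaging and how many are blank, and the SAP gives neither number. Any percentage would be invented.

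The conclusion rests on the text of the section 10.1 entries and assumes only that the sheet can hold a described result without a date or with a date outside the window.

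**What to change.** Reconcile the X-ray, CT, combined-imaging and Test for tuberculosis entries in section 10.1 so that the window already stated for X-ray and CT governs whether or not the box is checked:

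- dated inside the stated window: *implemented*;
- dated, but only outside the window: *not implemented in the window*;
- result described without a usable date: *implemented, date unknown*, on its own line;
- no entry: *unknown/not described*.

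State also where a checked box with neither date nor result belongs, since the present text leaves that open. Give Test for tuberculosis the same unknown class, say how the date-unknown line enters it, and add the matching rows to section 11 and Table 1.12.1.

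The cost is SAP wording and a few lines of derivation code. No new data are needed, and no test or analysis population changes.

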#### 4.2. Planning of survey

Any patients with gastro-intestinal Behcet disease (only those who did not respond to existing treatment) who receive this drug for defined indication for use and dosage and administration are included.

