Presence or absence of drug used for previously used drug (antibiotic)	Based on “161206 drug list_addtion (Fix)CRO”, if there is a data on previously used drug corresponding to relevant drug code or there is a check mark in a box for antibiotic in the survey sheet, patients are deemed to have previously received antibiotic and in any other situations, patients are deemed not to receive antibiotic.
Presence or absence of previously used drug (other drug)	Based on “161206 drug list_addtion (Fix)CRO”, if there is a data on “Other drugs than biological preparations” in the survey sheet and any data on previously used drug except for aminosalicylic acid preparation, steroid, immunomodulative drug, or antibiotic, patients are deemed to have previously received other drugs and in any other situations, patients are deemed not to have received other drugs.
Presence or absence of drug used for previously used drug (adalimumab)	Based on “161206 drug list_addtion (Fix)CRO”, if there is a data on previously used drug corresponding to relevant drug code, patients are deemed to have previously received adalimumab and in any other situations, patients are deemed not to have received adalimumab.
Presence or absence of previously used drug (infliximab)	Based on “161206 drug list_addtion (Fix)CRO”, if there is a data on previously used drug corresponding to relevant drug code, patients are deemed to receive infliximab and in any other situations, patients are deemed not to have previously received infliximab.
Presence or absence of previously used drug (other biological preparations)	Based on “161206 drug list_addtion (Fix)CRO”, if there is a data on “Biological preparations” in the survey sheet and any data on previously used drug except for adalimumab or infliximab, patients are deemed to have previously received other biological preparations and in any other situations, patients are deemed not to have previously received other biological preparations.

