Detailed classifications of medical history	tuberculosis, bacterial bronchitis, nontuberculous mycobacterial infection, aplastic anaemia, pancytopenia, malignant tumour, others
Previously used drug/previous treatment	Absent, present, unknown, not described
Classification of biological preparation as previously used drug/previous treatment	Adalimumab, infliximab, others
Classification of drugs other than biological preparation as previously used drug/previous treatment	Biological preparation, aminosalicylic acid preparation, steroid, immunomodulative drug, antibiotic, other previously used drug, operation, other previous treatment
Concomitant drug	Absent, present, unknown, not described
Detailed classification of concomitant drugs	Aminosalicylic acid preparation, oral adrenocortical steroid, immunomodulative drug, immunosuppressive drug, enteral nutrient, colchicine, others
Combination therapy	Absent, present, unknown, not described
Detailed classification of combination therapy	Operation, others
Endoscopy	Absent, present, unknown, not described

data	Method of dividing hierarchy
Detailed classifications of endoscopy	Ileocecum, colon, esophagus, others
Level of improvement in endoscopy findings	Remission or scar, shrinkage, no change, aggravation, not assessed
Evaluation of gastrointestinal symptoms	
0,1,2,3,4
 
0: No symptom
 
1: There was symptom in last 2 weeks but daily living activities were rarely disturbed.
 
2: There was symptom in last 2 weeks and daily living activities were slightly disturbed.
 
3: There was symptom in last 2 weeks and daily living activities were disturbed.
 
4: There was symptom in last 2 weeks and daily living activities were severely disturbed.

Detailed classifications of gastrointestinal symptoms	Abdominal pain, diarrhoea, others (including bloating, abdominal tenderness, haemorrhage)
Self-administration	Absent, present
Self-administration error	Absent, present, unknown, not described
Drug used after the discontinuation of this drug	Absent, present, unknown, not described
Detailed classifications of drug used after the discontinuation of this drug	Aminosalicylic acid preparation, steroid, immunomodulative drug, biological preparation, other drug
Level of overall improvement	Significant improvement, improvement, ineffective
Detailed classifications of level of overall improvement for patients with improvement or higher level of improvement	Significant improvement, improvement

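### The residual prior-drug rules (other biologics, other drugs) do not tie their two conditions to one drug record, and the prior-drug class rows code unknown history as non-use

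*SAP*

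**What the plan says.** All the rules at issue stand in SAP section 10.1.

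- Other biological preparations: the patient is a prior user "if there is a data on “Biological preparations” in the survey sheet and any data on previously used drug except for adalimumab or infliximab"; otherwise a non-user.
- Other drug: the patient is a prior user "if there is a data on “Other drugs than biological preparations” in the survey sheet" and there is "any data on previously used drug except for aminosalicylic acid preparation, steroid, immunomodulative drug, or antibiotic"; otherwise a non-user.
- Drug previously used (the parent item): within the section on earlier drugs and treatments, "data excluding that about previous treatment method is deemed to be previously used drug". If that section is empty and use cannot be judged, "where there is drug previously used is deemed to be unknown/not described".
- Class rows (adalimumab, infliximab, steroid, immunomodulative drug and so on): present if a coded record is found or, for the conventional classes, a box is ticked. Every other case is coded as not received.

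Section 11 splits prior biologics into "Adalimumab, infliximab, others" and lists other previously used drugs as a category beside biologics. Table 1.12.1 prints both classifications. Tables 2.9 and 3.4 test prior adalimumab, infliximab, steroid and immunomodulative drug, among other factors. Sections 9.2 and 9.5 keep unknown and not-described values out of tests.

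**The concern.** Each residual rule joins two conditions about the patient, and the second is not confined to the survey-sheet section named in the first. Different drugs can therefore satisfy the two halves, so a patient can be labelled a prior user of another biologic without having had one. Table 1.12.1 is where a reader learns how heavily pre-treated the population was. The notes to that table allow classes to overlap, so the categories need not sum to anything and a total would not expose the error.

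The second weakness is separate. One blank section makes the patient unknown on the parent item but a non-user on every class item. The survey admits "only those who did not respond to existing treatment", so a blank history is more plausibly missing information than proof of no earlier drug. These patients then sit in the comparison group of the class-level tests.

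**Working it through.** **Part 1: the residual rows.** The SAP gives no figure here to reproduce, so the check is logical. Inputs are the two rules and the definition of previously used drug in section 10.1. It is assumed that biologics are entered under the biologics heading and all other drugs under the other heading.

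Literal reading, at patient level:
- Other biologic = (at least one biologic entry) AND (at least one drug that is neither adalimumab nor infliximab).
- Other drug = (at least one non-biologic entry) AND (at least one drug outside the aminosalicylic acid, steroid, immunomodulative and antibiotic classes).

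Same-record reading: one and the same drug must meet both conditions.

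| Prior drugs | Other biologic / other drug, literal | Same record |
|---|---|---|
| Infliximab alone | no / no | no / no |
| Steroid alone | no / no | no / no |
| Infliximab + steroid | yes / yes | no / no |
| Adalimumab + steroid | yes / yes | no / no |
| Infliximab + aminosalicylic acid | yes / yes | no / no |
| Another biologic + steroid | yes / yes | yes / no |
| Infliximab + another non-biologic | yes / yes | no / yes |

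In the infliximab and steroid case, infliximab meets the first half of the biologic rule and the steroid the second. For the other-drug rule the roles swap, because biologics are not among the four excluded classes.

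Counting combinations:
- Adalimumab, infliximab and the four named classes give 2^6 = 64 combinations, none containing another biologic or another drug. Both flags are set whenever at least one of the two biologics and at least one named class are present: (2^2 − 1) × (2^4 − 1) = 3 × 15 = 45.
- Adding another biologic and another non-biologic gives 2^8 = 256. The biologic flag is wrong in 3 × (2^5 − 1) = 3 × 31 = 93, and the other-drug flag in 15 × (2^3 − 1) = 15 × 7 = 105.
- All discrepancies are false positives, since a drug meeting both conditions on one record also meets both at patient level.

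These are counts of drug combinations, not of patients. Neither residual flag appears in the factor lists of Tables 2.9 and 3.4, so no test uses them.

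**Part 2: unknown coded as non-use.** For a patient whose section is blank and cannot be judged:
1. The parent item is unknown/not described (10.1), so the patient is left out of any test of it (9.2, 9.5).
2. Each class row finds neither a coded record nor a tick, and codes the patient as not received.
3. That is not an unknown value, so the exclusion in 9.2 and 9.5 does not catch it. The patient enters the class-level tests in Tables 2.9 and 3.4 as a non-user.

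The size needs two figures that the SAP does not give: m, the share of undescribed sections, and p, the prevalence of prior use, taken as equal in described and undescribed patients. The group coded as non-users is (1 − m)(1 − p) + m = (1 − p) + mp, of which mp are users. The misclassified share is f = mp / [(1 − p) + mp].

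| Assumed p | m = 0.05 | m = 0.20 |
|---|---|---|
| 0.2 | 0.01/0.81 = 1.2% | 0.04/0.84 = 4.8% |
| 0.4 | 0.02/0.62 = 3.2% | 0.08/0.68 = 11.8% |
| 0.7 | 0.035/0.335 = 10.4% | 0.14/0.44 = 31.8% |

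If being undescribed is also unrelated to outcome, the observed risk difference is (1 − f) times the true one. With m = 0 there is no effect.

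**The case against.** The strongest reply is that the residual rules can be read record by record. Both rows open with the coded drug list, the SAP often uses the word data for individual records, and the row name and the section 11 split show what was meant. On that reading the flags are correct. This stands as a possible reading, but the text does not state it. The neighbouring rows ask only whether something exists for the patient, and neither residual rule refers to a relevant drug code as its neighbours do. The drug list itself is not available to settle the matter.

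A reader might infer that the flags distort the safety or efficacy factor analyses. They do not, because those analyses do not list them. A reader might also put a figure on the affected patients: with 20–40% prior adalimumab or infliximab use, half to all of it alongside a conventional drug, 0.2 × 0.5 = 10% to 0.4 × 1.0 = 40% of patients. Every input there is assumed, and the product applies only if the literal rule is programmed. The error might also be noticed: if nearly every prior biologic user also had a conventional drug, the residual biologic count would approach the count of all prior biologic users.

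On blank sections, the notes to Table 1.12.1 take each breakdown as a rate of the item one level higher, which largely keeps unknowns out of the descriptive class rates. Section 9.5 also states the right principle for tests. What remains is that the class rows never produce the unknown category on which that principle depends.

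**Conclusion.** The point holds in two limited parts. First, as worded, the two residual rules give false positives for any patient with adalimumab or infliximab plus a drug from a named conventional class. This depends on the literal reading being programmed, is confined to two descriptive rows of Table 1.12.1, and cannot be sized in patients from the SAP. It is an ambiguity in a programming rule, not proof that the reported table is wrong.

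Second, coding unknown history as non-use conflicts with sections 9.2 and 9.5 and reaches the Table 2.9 and 3.4 tests of prior adalimumab, infliximab, steroid and immunomodulative drug. Under the assumptions shown, the misclassified share of the comparison group runs from about 1% to 32%, rising with the prevalence of prior use and the rate of blank sections. The range illustrates sensitivity and is not an estimate. If few sections are blank, the effect is negligible.

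**What to change.** Reword the two residual rows in section 10.1 so that one record must meet both conditions:
- other biologic: a drug recorded under Biological preparations that is neither adalimumab nor infliximab;
- other drug: a drug recorded under the non-biologic heading that belongs to none of the four named classes.

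In all prior-drug class rows, assign unknown/not described whenever Drug previously used has that value, and leave those patients out of the class-level tests as 9.2 and 9.5 already intend.

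The cost is two reworded conditions and one inherited category, with no new data. The drawback is slightly fewer patients in the prior-drug tests.
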